8.2.2.4 Abnormal Laboratory Values

If an abnormal laboratory value or vital sign is associated with clinical signs and/or symptoms, the sign or symptom should be reported as an AE or SAE, and the associated laboratory value or vital sign should be considered additional information and collected on the relevant eCRF. If the laboratory abnormality is a sign of a disease or syndrome, only the diagnosis needs to be recorded on the eCRF (and SAE Report Form, if applicable). Abnormal laboratory values will be reported as an AE if the laboratory result:

- requires an adjustment in the trial drug(s) or discontinuation of treatment
- require additional testing or surgical intervention
- is associated with accompanying symptoms
- is considered to be an AE by the investigator

8.2.2.5 New Cancers

The development of a new primary cancer should be regarded as an AE and will generally meet at least one of the serious criteria (see [Section 8.1](#)). New primary cancers are those that are not the primary reason for the administration of the trial treatment and have developed after the inclusion of the subject into the trial. They do not include metastases of the original cancer.

Progression of the disease under study (disease progression) is not an AE/SAE, unless fatal.

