- g. Additional scans may be performed (eg, head/neck CT) if clinically indicated or if the area is a site of known disease. Magnetic resonance imaging (MRI) may be substituted if clinically indicated, but the modality chosen to evaluate each individual subject should be the same throughout the duration of the study.
- h. Bone marrow biopsy and/or aspirate are required at Screening as a baseline for response assessment (unless clinically contraindicated). Sample and corresponding pathology report should be sent for biomarker analysis if available.
- i. For all subjects AEs should be monitored from time of the signing of the ICF. Any new medical or worsening preexisting conditions arising after signing the ICF will be captured as an AE for randomized subjects. SAEs for all subjects will be reported from the signing of the ICF as defined in [Section 8.1.3](#).
- j. Dosing should occur within 1 week of randomization after all screening assessments have been obtained and eligibility confirmed.

Table 2: Schedule of Assessments for Subjects Receiving Duvelisib ^a

	Cycle 1 (21±2 days) ^o		Cycle 2 (28±4 days) ^o		Cycles 3 – 7 (28±4 days) ^o	Cycle 9-19 every odd cycle (28±4 days) ^o	> Cycle 19 every odd cycle (28±4 days) ^p	Early Treatment Termination (ETT) from Duvelisib ^q	Safety Follow-up
	D1	D8±2	D1±2	D15±2	D1±4	D1±4	D1±4	≤7 d from last dose	30+7 d from last dose
Concomitant medications & Procedures	X	X	X	X	X	X	X	X	X
AE/SAE assessment ^b	X	X	X	X	X	X	X	X	X
Focused physical examination	X		X		X	X	X	X	
Blood chemistry ^c	X ^d	X	X	X	X	X	X	X	
Hematology ^c	X ^d	X	X	X	X	X	X	X	
Coagulation tests ^c	X ^d								
Serum Immunoglobulins	X				X ^e	X ^e		X ^e	
βhCG pregnancy test ^{c, f}					X	X	X	X	
Blood for Cytogenetics/FISH analysis ^g	X ^{h, i}								
Blood for IGHV mutation analysis ^g	X ^h								
Blood for Immunophenotyping ^{g, j}	X ^k				X ^e	X ^e		X ^e	
Serum for biomarkers ^{g, j}	X ^k		X		X ^e	X ^e		X ^e	
Blood for biomarkers ^g	X ^k		X		X ^e	X ^e		X ^e	
Pharmacogenomics ^g	X ^l								
EQ-5D & FACIT-F	X ^d				X ^m	X ^m	X ^m	X ^m	
ECOG Performance status	X ^d	See Table 5: Disease Response Assessments							

Response assessments		See Table 5: Disease Response Assessments	
Archival tumor tissue	X ⁿ		
Study drug administration	X	Continuous Dosing	

- a. See [Section 6.2](#) and [6.3](#) for additional information on each assessment.
- b. AEs are collected (and SAEs reported) through 30 days post last dose of duvelisib.

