	Cycle 1 (21±2 days) °			Cycle 2 (28±4 days) °				Cycle 3-7 (28±4 days) °	Early Treatment Termination (ETT) ⁿ from Ofa ≤ 7 d from last dose	Safety Follow-up Visit 30+7d from last dose	Clinical Assessment Period ° C9-C19 (28±4 days) Day 1±4
	Ofa 300 mg D1	Ofa 2000 mg D8±2	Ofa 2000 mg D15±2	Ofa 2000 mg D1±2	Ofa 2000 mg D8±2	Ofa 2000 mg D15±2	Ofa 2000 mg D22±2	Ofa 2000 mg D1±4			
Study drug administration	X	X	X	X	X	X	X	X			

- a. See [Section 6.2](#) and [6.3](#) for additional information on each assessment.
- b. AEs are collected (and SAEs reported) through 30 days post last dose of ofatumumab.
- c. Additional (unscheduled) assessments should be done as clinically indicated. Blood samples should be drawn and results reviewed within 72 hours of the designated clinic visit.
- d. Screening evaluations performed within 7 days of Cycle 1 Day 1 can be used and assessments don't need to be repeated at Cycle 1 Day 1 (predose)
- e. Drawn at Day 1 of Cycles 3, 5, 7, 11, 15, 19, and ETT. Blood for immunophenotyping, serum for biomarkers, and blood for biomarkers does not need to be collected beyond the ETT visit or treatment discontinuation
- f. May be either urine or serum, and will be performed every odd cycle while on treatment.
- g. To be sent to the central laboratory.
- h. This sample may be drawn at screening or Cycle 1 Day 1 (predose). Collection at Cycle 1 Day 1 is preferred. If drawn at screening, a sample is not needed at Cycle 1 Day 1.
- i. This sample will be analyzed centrally and is separate from the documentation of prior del(17p) analysis required for eligibility and stratification.
- j. Samples on Cycle 1 Day 1 should be drawn predose.
- k. Pharmacogenomics sample (buccal swab) is optional.
- l. QoL assessments to be captured on Day 1 of Cycles 3, 5, 7, 11, 15, and 19, until disease progression, subject withdrawal, or initiation of additional anticancer therapy and when possible, at the ETT (if >1 month from last administered questionnaire).
- m. Requests for archival tissue (pretreatment sample) should be initiated at Cycle 1 Day 1. In the event a request is placed but no archival tissue can be located, this sample type is not required.

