- n. The Early Treatment Termination (ETT) Visit should occur for any subject who discontinues ofatumumab treatment prior to Cycle 7 Day 1. ETT assessments need not be performed for those assessments performed within the previous 2 weeks (previous 30 days for Disease Response Assessments [see [Table 5](#)] and the QoL assessment).
- o. The clinical visit schedule should be maintained until Cycle 9 for subjects who discontinue study treatment prior to Cycle 9 for reasons other than PD. The clinical assessment period then begins at Cycle 9, with visits occurring every other month until disease progression, subject withdrawal, or initiation of additional anticancer therapy; no additional study drug (ofatumumab) will be administered.

Table 5: Disease Response & Follow-up Assessments for All Subjects

Assessments ^d	Screening (baseline)	Cycle 3 Day 1	Cycles 5, 7, 11, 15, & 19 Day 1	Early Termination from Study Treatment (ETT) ^a ≤7 days of last dose	Disease Follow-up ^b Every 6 months (±4 weeks)	Survival Follow-up ^c Every 6 months (± 4 weeks)
CT scans of chest, abdomen and pelvis ^e	X	X	X	X	X	
Bone marrow biopsy and/or bone marrow aspiration ^f	X	X	X	X	X	
Complete blood count (CBC) and differential count ^g	X	X	X	X	X ⁱ	
Blood sample for assessment for minimum residual disease (MRD) ^h		X	X	X	X	
Focused physical examination ^g , disease related constitutional symptoms assessment, and ECOG performance status	X	X	X	X	X	
Survival						X

- a. ETT Disease Response Assessment is not necessary if a Disease Response Assessment was performed within the previous 30 days. In the absence of disease progression or initiation of subsequent anticancer therapy, all subjects with ETT prior to Cycle 19 Day 1 will maintain the disease response assessment schedule (Cycles 5, 7, 11, 15, & 19)
- b. All subjects with no disease progression by Cycle 19 Day 1 will continue Disease Response Assessments (Section 6.5.3.1) every 6 months until disease progression, subject withdrawal, or initiation of additional anticancer therapy. The first disease follow-up assessment after Cycle 19 Day 1 should occur approximately 6 months after last disease assessment.
- c. All subjects will have Survival Follow-up for up to 6 years after randomization or until death. This assessment can be conducted by telephone interview. Information on initiation of other anticancer therapy (including start date, therapy type, and response on treatment) will also be collected.

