4.1 SCHEDULE OF ADMINISTRATION

Subjects who meet all the eligibility criteria at Screening will return to the clinic on Day 1 to receive their first dose of study drug (either duvelisib or ofatumumab). The first treatment cycle for each treatment arm will be 3 weeks (21±2 days). Subsequent treatment cycles will be 4 weeks (28±4 days).

Arm 1 (Duvelisib): Subjects randomized to duvelisib will receive their first dose of study drug in clinic on Day 1, initiating Cycle 1 of treatment. These subjects will return for a second clinical visit on Day 8±2. Cycle 1 will be 21 days, with all subsequent cycles 28 days in length. Cycle 2 will have clinic visits on Day 1 and on Day 15±2. Each subsequent cycle (Cycle 3-7) and then every odd cycle (Cycle 9 to 19) will have only one clinic visit on Day 1. Subjects will receive duvelisib continuously for 18 cycles or until disease progression or unacceptable toxicity, whichever comes first. After completing approximately 18 cycles of treatment with duvelisib, subjects who, in the judgment of the investigator, may derive benefit from continued treatment may receive additional cycles of duvelisib until disease progression or unacceptable toxicity. However, to receive additional cycles of duvelisib beyond 18 cycles, subjects must have CLL/SLL requiring treatment by Cycle 19 Day 1 (Reference 4.2.1.2). Subjects who receive duvelisib beyond 18 cycles (Cycle 19 Day 1) will maintain clinical visits every odd cycle (Cycle 21, 23, etc) until disease progression, subject withdrawal, or initiation of additional anticancer treatment. After Cycle 18, disease response assessments will continue every 6 cycles for those subjects who have not had disease progression, withdrawn consent, or initiated additional anticancer treatment.

Arm 2 (Ofatumumab): Subjects randomized to ofatumumab will receive IV treatment according to the approved prescribing information.^{10, 11} Subjects will receive 8 weekly IV infusions, starting with an initial dose of ofatumumab of 300 mg followed by seven weekly doses of 2000 mg. Thereafter, subjects will receive 2000 mg ofatumumab once every cycle for four cycles or until disease progression or unacceptable toxicity, whichever comes first.

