8.2 PROCEDURES FOR ELICITING, RECORDING, AND REPORTING ADVERSE EVENTS

8.2.1 Eliciting and Recording Adverse Events

Subjects will be instructed to report all AEs and will be asked a general health status question at each study visit. All AEs occurring in randomized subjects will be recorded in the eCRF from the time of ICF until 30 days after the last dose of study treatment. An AE will be followed until it is either resolved, has returned to baseline, or is determined to be a stable or chronic condition. All SAEs occurring from the signing of ICF through 30 days post last study drug will be processed as outlined in [Section 8.2.3](#).

At each required visit during the trial, all AEs that have occurred since the previous visit must be reviewed. The Investigator or appropriate designee must determine if the adverse event is serious or non-serious.

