8.2.3 Reporting of Serious Adverse Events

8.2.3.1 Immediate Reporting of Serious Adverse Events by Investigator to Sponsor

All SAEs (including SAEs occurring in screen failure and randomized subjects) will be reported to the Sponsor or designee within 24 hours of the Investigator's first knowledge of the event, even if the experience does not appear to be related to duvelisib or ofatumumab, from the time of signing ICF through 30 days after the last dose of study drug.

Serious adverse events should be communicated on an SAE report form as follows:

- Email: [contact]
- Hotline (Phone): [contact] (USA)
- [contact] (USA)
- For international numbers, please refer to the SAE Report Form and supporting documentation.

The initial SAE report must be as complete as possible, including details of the current illness and (serious) AE, and an assessment of the causal relationship between the event and the investigational product(s). Information not available at the time of the initial report (eg, final diagnosis, an end date for the AE, or relevant laboratory values received after the report) must be documented on a follow-up SAE Report Form. All SAE follow-up information must be reported in the same timelines as initial information (ie, within 24 hours of the investigator's first knowledge of information).

At any time after completion of the AE reporting period (ie, 30 days post-treatment), if an Investigator becomes aware of an SAE that is suspected by the Investigator to be related to study drug, the event must be reported as described above.

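### Systematic collection of new primary cancers ends 30 days after last dose: about month 6.3 on ofatumumab, but treatment length plus 30 days on duvelisib

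*Protocol*

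**What the plan says.** **Definition.** Protocol 8.2.2.5 states: "The development of a new primary cancer should be regarded as an AE and will generally meet at least one of the serious criteria". It counts cancers arising after inclusion and gives no end date: "New primary cancers are those that are not the primary reason for the administration of the trial treatment and have developed after the inclusion".

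**Collection window.** Under Protocol 8.2.1, AEs in randomized subjects "will be recorded in the eCRF from the time of ICF until 30 days after the last dose of study treatment". The schedules repeat this for each arm. Table 2 note b: "AEs are collected (and SAEs reported) through 30 days post last dose of duvelisib". Table 4 note b: "AEs are collected (and SAEs reported) through 30 days post last dose of ofatumumab".

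**After the window.** Protocol 8.2.3.1 keeps one express route open, with no time limit: an event must still be reported "if an Investigator becomes aware of an SAE that is suspected by the Investigator to be related to study drug".

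**Visits.** Table 4 leaves the AE/SAE row unmarked in the Cycle 9 to 19 Clinical Assessment Period. It does mark concomitant medications and procedures, focused examination, chemistry and hematology there. Table 2 marks AE/SAE assessment at the same cycles for duvelisib. Disease Follow-up (6.5.3.1) includes CT and focused examination every 6 months for subjects without progression. Survival contacts are long: "All subjects will have Survival Follow-up for up to 6 years after randomization or until death". They list only survival and other anticancer therapy (Table 5 note c; 6.5.3.2).

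**Analysis.** SAP 7.3.1 (version 4.0) counts TEAEs to 30 days after last dose. It plans no exposure-adjusted rates and no table of new cancers. Its only equal-window AE tables cover onset within 24 weeks of first dose.

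**The concern.** The time during which a new cancer is actively looked for depends on how long the subject is treated, and treatment length differs between arms by design. A crude by-arm incidence then compares windows of different length. If the true rates were equal, the arm treated longer would still show more cancers.

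What is left after the window is passive. The investigator has to learn of the cancer and suspect the drug, knowing the assignment in an open-label trial. That cannot be expected to work alike in the two arms.

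At stake is the readability of one safety comparison. The sponsor could face an apparent signal against its own drug that the window produced, and later cancers in either arm could go unrecorded although subjects are contacted for years.

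**Working it through.** Month = 365.25/12 = 30.44 days.

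**1. The plan's own figure.** Protocol 4.2.2 puts the 12 infusions within 6 to 7 months. With a 21-day first cycle and 28-day later cycles (4.1), doses fall on Days 1, 8, 15, 22, 29, 36, 43, 50, 78, 106, 134 and 162, which is 12 doses. Seven cycles are 21 + 6×28 = 189 days = 6.2 months. The figure reproduces.

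**2. When the window closes.**
- Ofatumumab, full course: Day 162 + 30 = Day 192, or 191/30.44 = 6.3 months after Day 1 (5.6 to 7.0 if every cycle runs to its limit in one direction). That is 6.3/72, about 9% of the 6-year survival follow-up.
- Duvelisib, 18 cycles: 21 + 17×28 = 497 days = 16.3 months; plus 30 days, 17.3 months. It is later if treatment continues, and 30 days after last dose if treatment stops early.
- Cycle 19 Day 1 is Day 498. From Day 192 that leaves 306 days, about 10 months, of scheduled ofatumumab visits with no AE/SAE assessment marked.

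**3. Share of events inside the window at 27.5 months.** From the documents: PFS exponential with medians of 9 and 15 months, peak accrual of 30 per month after an 11-month ramp-up, enrollment complete at 16 months, final PFS analysis at 27.5 months. Assumed: a linear ramp, the same constant event rate in both arms, follow-up to the cutoff for everyone (no deaths or dropout), and treatment stopping only at progression or at the ofatumumab cap. With a constant rate, the share of events equals mean window divided by mean follow-up.
- Mean follow-up: the ramp enrolls 11×30/2 = 165 at a mean entry of 7.33 months; the next 5 months enroll 150 at a mean of 13.5. Mean entry is (165×7.33 + 150×13.5)/315 = 10.27, so mean follow-up is 27.5 − 10.27 = 17.2 months. Stopping at exactly 300 subjects gives 17.5 months and the same ratio.
- Ofatumumab: rate ln2/9 = 0.0770, cap 161/30.44 = 5.29 months. Mean window = (1 − e^(−0.0770×5.29))/0.0770 + 0.99 = 4.34 + 0.99 = 5.33 months. Share 5.33/17.2 = 31%.
- Duvelisib: rate ln2/15 = 0.0462. For follow-up F, mean window = 0.99 + (1 − e^(−0.0462(F − 0.99)))/0.0462. Averaged over accrual this is 12.26 months. Share 12.26/17.2 = 71%.
- Ratio 12.26/5.33 = 2.3. With every duvelisib subject stopped at 18 cycles, the mean window is 11.62 months and the ratio 2.2.

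**4. Sensitivity to stops other than progression.** The documents give no rate, so exponential stops with a mean of 24 or 12 months are assumed.
- On duvelisib only: mean window 9.50 or 7.66 months; ratio 9.50/5.33 = 1.8 or 7.66/5.33 = 1.4.
- In both arms: the ofatumumab rate becomes 0.0770 + 1/24 = 0.1187 or 0.0770 + 1/12 = 0.1604. The same capped formula gives 4.91 or 4.55 months, and ratios of 1.9 or 1.7.

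**5. Counts.** The documents give no cancer rate. At an assumed 1% to 3% per year and 150 subjects per arm, expected events inside the window are 150×0.01/12×12.26 = 1.5 to 4.6 on duvelisib, and 150×0.01/12×5.33 = 0.7 to 2.0 on ofatumumab. The gap is about 1 to 3 subjects.

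**The case against.** A reader might infer that 8.2.2.5 contradicts the 30-day window, or that the arms follow different rules. Neither is so. Section 8.2.2.5 sits among instructions for recording AEs, and its reference to inclusion separates new cancers from pre-existing ones. The window is set elsewhere, is a familiar convention, and is identical in both arms. The imbalance comes from treatment length.

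A reader might also infer that a cancer after the window is seen only if the investigator blames the drug. The documents give other routes. Protocol 6.3.1.1 has new clinically significant examination findings at the Table 2 and Table 4 visits recorded as AEs. Protocol 8.2.1 has AEs reviewed at each required visit. Concomitant medications and procedures are collected at Cycles 9 to 19, Disease Follow-up includes CT and examination, survival contacts record other anticancer therapy, and the SAP summarizes deaths during follow-up. These routes stand, but capture is partial and unsystematic. Sections 6.3.1.1 and 8.2.1 also sit badly with the unmarked row in Table 4, so sites could follow either. An AE with onset beyond 30 days would not be a TEAE in any case.

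It can also be said that the bias runs against the experimental drug, that the SAP reports exposure by arm, and that the 24-week tables give an equal window. All true. But exposure summaries do not correct the cancer counts, and the 24-week tables equalise the window only for early events.

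Finally, the problem is generic to any event counted over unequal exposure, and the documents do not name new cancers as a risk of either drug or say that they occur late. The point should not rest on such a premise, and it does not need to: a constant rate is enough.

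**Conclusion.** The point holds as a limited weakness in safety ascertainment. Collection of new primary cancers regardless of causality ends 30 days after last dose: about month 6.3 on a full ofatumumab course, against about month 17.3 or later on 18 or more cycles of duvelisib.

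Under equal true risk the by-arm TEAE tables would show a spurious duvelisib excess. Its size is about 2.3-fold if duvelisib stops only at progression, and about 1.4 to 1.8-fold with assumed stops on duvelisib at a mean of 12 to 24 months. These figures rest on a constant rate, a linear accrual ramp, the planning medians and complete follow-up to 27.5 months. The direction does not depend on the exact values, provided that duvelisib subjects are treated longer on average.

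Absolute counts would be small, a difference of perhaps 1 to 3 subjects at an assumed 1% to 3% per year. No sample size, power, alpha or efficacy endpoint is touched. The case for change is that the correction is cheap and the plan as written does not make it.

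**What to change.** - **Protocol 8.2.2.5, Tables 4 and 5.** Record new primary cancers in both arms, regardless of attribution or time since last dose, at the existing Clinical Assessment, Disease Follow-up and Survival Follow-up contacts.
- **Protocol 6.3.1.1, 8.2.1 and Table 4.** Reconcile the examination and visit-review sentences with the unmarked AE/SAE row at Cycles 9 to 19, so that sites follow one rule.
- **SAP 7.3.1.** Add one table of new primary cancers by arm from first dose, with person-time, split into before and after new anticancer therapy. Crossover to the opposite study drug in the extension protocol counts as new therapy.

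The cost is a protocol amendment, one question at contacts already scheduled, one eCRF field and one table. Cancers after crossover or other therapy are hard to attribute to the randomized drug, which is why the split is needed.

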8.2.2.6 Medication Errors, Misuse and Abuse of Study Drug

Overdose, medication error, misuse and abuse are defined as follows:

- *Overdose*: refers to the administration of a quantity of study drug given per administration or cumulative, which is above the maximum dose according to the protocol. Clinical judgment should always be applied.
- *Medication error*: refers to an unintentional error in dispensing or administration of study drug not in accordance with the protocol.

- *Off-label use*: relates to situations where the study drug is intentionally used for medical purpose not in accordance with the protocol.
- *Misuse*: refers to situations where the study drug is intentionally and inappropriately used not in accordance with the protocol.
- *Abuse*: corresponds to the persistent or sporadic, intentional excessive use of the study drug, which is accompanied by harmful physical or psychological effects.
- *Occupational exposure*: refers to the exposure to the study drug as a result of one's professional or non-professional occupation.

Overdoses, medication errors, abuse or misuse will be collected as part of investigational medicinal product dosing information and/or as a protocol violation, as required.

Any AE associated with an overdose, medication error, misuse or abuse of study drug should be recorded on the AE eCRF with the diagnosis of the AE.

